2.2 Secondary Objective

2.2.2 **In a pragmatic trial, estimate the effect of mPATH-CRC on completion of CRC screening within 16 weeks of visit.** We will query the electronic health record (EHR) at each study clinic to identify individuals aged 50 – 74 with no evidence of current CRC screening at the time of their clinic visit. We will then examine in the EHR whether these individuals complete CRC screening within 16 weeks of their index visit. The primary effectiveness analysis will compare the proportion of patients who complete screening between the pre- and post-implementation period in the “high touch” vs. “low touch” clinics. A secondary analysis will explore whether there is a dose-response relationship between use of mPATH-CRC and screening rates across all clinics.

2.2.3 **Determine the factors that facilitate or impede the maintenance of mHealth interventions like mPATH-CRC.** We will assess all clinics 12 months after implementation to identify those with high, low, and variable levels of maintenance. Using mixed methods that incorporate in-depth interviews with clinic staff, providers, and administrators, we will identify theory-based and organizational factors associated with sustained use of technology-based

EFFECTIVENESS AND IMPLEMENTATION OF MPATH-CRC: A MOBILE HEALTH SYSTEM FOR

COLORECTAL CANCER SCREENING

Wake Forest Baptist Comprehensive Cancer Center (WFBCCC)

WFBCCC # TBD

interventions like mPATH-CRC. These results will provide critical information to guide future large-scale dissemination and implementation trials.

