5.2 Primary Outcome

mPATH-CRC Reach: Proportion of all Spanish or English-speaking patients, ages 50 – 74, who are eligible for CRC screening and complete the mPATH-CRC program in the 6th month (weeks 21 – 24) following the implementation date. Patients who use mPATH™-CheckIn and are told they are due for CRC screening but advised to discuss screening with their doctor due to detected risk factors are also counted as having used mPATH™-CRC.

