6.0 Analytic Plan

6.1 Sample Size and Power

6.1.1 Primary outcome: Our primary objective is to assess differences in mPATH-CRC Reach proportion of participants who complete the mPATH-CRC program or have risk factors identified by mPATH-CheckIn) in the 6th month between the two implementation strategies. Using formulae found in Hemming et al.,⁷² **Table 3** shows the number of clinics necessary to detect differences in Reach ranging from .15 to .20 with 80% and 90% power for intraclass correlations (ICC) ranging from .03 to .08, assuming an average sample size per clinic of 30 with a cluster sample size coefficient of variation (CV) of 25%. These latter numbers are based on estimated numbers of eligible patients seen monthly, obtained from a

survey of the participating clinics. Since these data will be obtained from the EHR,

Table 3. Total number of clinics needed to detect the specified difference in Reach as a function of the power, ICC, and difference.

| Diff/ICC | 80% Power | | | | | | 90% Power | | | | | |
|----------|-----------|-----|-----|-----|-----|-----|-----------|-----|-----|-----|-----|-----|
| | .03 | .04 | .05 | .06 | .07 | .08 | .03 | .04 | .05 | .06 | .07 | .08 |
| .15 | 22 | 26 | 29 | 33 | 36 | 40 | 30 | 34 | 39 | 44 | 48 | 53 |
| .20 | 12 | 14 | 16 | 18 | 20 | 22 | 16 | 19 | 22 | 24 | 27 | 29 |

we will use all eligible patients at each site. We will recruit a total of 22 clinics, which will provide at least 80% power to detect a difference of 15% if the ICC is 0.03 or lower. If the ICC were as high as 0.08, we would have over 80% power to detect a difference of 20%. These calculations assume average utilization across all sites of 50%. Power increases as rates move away from 50% in either direction.

6.1.2 Effectiveness outcome: A secondary objective is to assess the effect of mPATH-CRC on screening rates (effectiveness) comparing 8 months of data prior to implementation to 8 months of data following implementation. The detectable difference (difference in screening rates pre vs post) depends on the sample size, power, ICC, and cluster sample size CV. We will assume a screening rate in the pre-implementation group of 15%, as observed in the control group in our R01 study.⁴⁵ Using SS/Power formulae for cluster designs^{72,73}, **Table 4** shows the differences in screening rates we will be able to detect

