with 80% and 90% power for ICCs ranging from 0.03 to 0.06, assuming an average monthly sample size of 30 patients per clinic in the EHR, a cluster sample size CV of 25%, and no change in the screening trends over time. Because of the diminishing return of cluster designs, additional patients have little effect on the detectable difference, although we will use all the patients in the EHR. We see that we will be able to detect a 10% difference in screening rates (15% vs 25%) with 80% power even if the ICC is as large as 0.04. We estimate that a minimum of 30 patients per clinic per month will meet inclusion criteria for this analysis (based on age, language, and screening status) and will be available through the EHR, so we will be amply powered for assessing the secondary aim.

To evaluate whether the effect of mPATH-CRC on screening rates differs by implementation strategy, the period (pre vs post) by strategy (“high touch” vs “low touch”) interaction can be evaluated. Based on the control group from the previous randomized-controlled efficacy study, we anticipate a screening rate of 15% for “low touch” and pre- implementation. An increase in

Table 4. Detectable difference in screening rates as a function of the Power and the ICC (22 Clinics)

| ICC | 80% Power | | | | 90% Power | | | |
|-----|-----------|------|------|------|-----------|------|------|------|
| | .03 | .04 | .05 | .06 | .03 | .04 | .05 | .06 |
| | .087 | .100 | .113 | .125 | .102 | .118 | .133 | .146 |

EFFECTIVENESS AND IMPLEMENTATION OF MPATH-CRC: A MOBILE HEALTH SYSTEM FOR

COLORECTAL CANCER SCREENING

Wake Forest Baptist Comprehensive Cancer Center (WFBCCC)

WFBCCC # TBD

the screening rate from 15% to 25% from pre to post, corresponds to an odds ratio (OR) of 3.

Similarly, assuming a screening rate in the “low touch” group of 15%, and a screening rate of 25% in the “high touch” group, also corresponds to an OR of 3. By design, we anticipate half of the patients being in the “high touch” group and half in the post period, and that strategy and period are independent. Based

on these assumptions, **Table 5** shows the interaction OR that can be detected with 80% power for ICCs ranging from 0.03 to 0.06, assuming an average monthly sample size of 30 patients per clinic in the EHR (for 8 months pre and 8 months post), a cluster sample size CV of 25%, and no change in the screening trends over time.

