6.3 Analysis of Secondary Outcomes

The key secondary outcome of effectiveness of mPATH-CRC will be evaluated by comparing the proportion who complete CRC screening within 16 weeks of their index visit to the clinic between a pre-implementation cohort (months 12 - 4 before implementation) and a post-implementation cohort (months 1 - 8 after implementation). Similar to the model described for mPATH-CRC Reach above, effectiveness of mPATH-CRC will be evaluated using a mixed effects logistic regression model. For an overall assessment of the effectiveness, completing CRC screening within 16 weeks (Y/N) will be the patient-level outcome, implementation cohort will be the primary independent variable, site will be a random effect, and the stratification factor clinic size will be a covariate per the design. Pre- vs post-implementation changes will also be compared between the “high touch” and “low touch” implementation strategies and between dose levels defined based on mPATH™-CRC usage by incorporating interactions into the mixed effects logistic regression models. An interrupted time series analysis (segmented

EFFECTIVENESS AND IMPLEMENTATION OF MPATH-CRC: A MOBILE HEALTH SYSTEM FOR

COLORECTAL CANCER SCREENING

Wake Forest Baptist Comprehensive Cancer Center (WFBCCC)

WFBCCC # TBD

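### Section 6.3 tests dose-response by comparing undefined usage levels; entering clinic usage as a continuous variable would keep more information from 22 clinics and give a slope.

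*Combined protocol and SAP*

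**What the plan says.** Section 2.2 (objective 2.2.2) sets the aim: "A secondary analysis will explore whether there is a dose-response relationship between use of mPATH-CRC and screening rates across all clinics". Section 6.3 gives the method in one clause. Pre/post changes in screening will be compared between the two implementation strategies and also "between dose levels defined based on mPATH™-CRC usage by incorporating interactions into the mixed effects logistic regression models".

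That clause is all the plan says on the method. It does not give the number of levels, the cut-points, the usage measure, the time window, or whether dose belongs to the clinic, the provider or the patient. It names no trend test and no continuous-usage analysis, and Section 6.1 gives no power for this question.

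Usage itself is measured as a proportion. Section 5.2 defines Reach as "Proportion of all Spanish or English-speaking patients, ages 50 – 74, who are eligible for CRC screening and complete the mPATH-CRC program" in month 6, and Section 5.3 repeats it for other months. The plan does not say that Reach is the dose variable.

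**The concern.** A dose that interacts with period must be assigned to patients in both cohorts. Pre-launch patients never had the chance to use mPATH-CRC, so a patient-level dose cannot fill that role. A clinic-level dose can, and it fits the across-all-clinics wording of objective 2.2.2. This is an inference; the documents do not state it.

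On that reading, the analysis takes 22 values between 0 and 1 and sorts them into levels. Clinics within a level are treated as having the same dose. If the relationship is roughly linear, the spread within levels carries information that is lost. A comparison of levels also does not give the quantity a dose-response question asks for, which is the change in screening per unit of use. Because the levels are undefined, the cuts could be chosen after the data are seen, and the answer could depend on them.

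Both arms receive mPATH, so variation in use is one of the few ways the trial can link actual use to screening.

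**Working it through.** **The plan's own figure.** No power is stated for the dose-response test. The nearest figure is Table 3: 22 clinics for 80% power at a Reach difference of 0.15 and ICC 0.03. Take m = 30, CV = 0.25, rates 0.575 and 0.425, and two-sided 5% (assumed; alpha is not stated).
- Design effect = 1 + ((1 + 0.25²)×30 − 1)×0.03 = 1.926.
- Patients per arm before inflation = (1.960 + 0.842)² × 2 × 0.575 × 0.425 / 0.15² = 170.5.
- Clinics = 2 × 170.5 × 1.926 / 30 = 21.9, which agrees with 22.

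The ICC range and Reach differences in Table 3 can therefore be reused to describe how much usage varies between clinics.

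**Inputs from the documents.**
- 22 clinics, CV 25%, mean use 50%, Reach ICC 0.03 to 0.08, Reach difference 15 or 20 points, pre-launch screening rate 15% (Section 6.1).
- Effectiveness cohort: "assuming an average monthly sample size of 30 patients per clinic in the EHR" for 8 months each side, so 30 × 8 = 240 per clinic per period.
- 15% versus 30% screening in the previous efficacy trial (Section 1.0).

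**Assumptions.** Screening rises linearly by 15 points from zero to full use. Usage is normal within arm. The clinic-by-period SD is 0 or 2 points. The test is at clinic level, two-sided 5%.

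**Hand calculation** (ICC 0.03, difference 0.15, SD 0).
- SD of usage = √(ICC×0.25 + (0.15/2)²) = √(0.0075 + 0.005625) = 0.115.
- Post rate at mean use = 0.15 + 0.15×0.5 = 0.225.
- Variance of a clinic's change = (0.15×0.85 + 0.225×0.775)/240 = 0.001258.
- Signal z = 0.15×0.115/√(0.001258/22) = 2.27.
- Continuous power = Φ(2.27 − 1.96) = 62%.
- Median split (efficiency 0.637 for normal usage) = Φ(2.27×√0.637 − 1.96) = 44%.
- Three-level trend (efficiency 0.793) = Φ(2.27×√0.793 − 1.96) = 53%.

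The loss is about 18 points for the median split and 10 for the trend score. Absolute powers run a little high because this uses the normal rather than t on 20 df and equal clinic sizes.

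**Simulation** (5,000 replicates per setting, F tests on clinic changes weighted by clinic size, 15-point slope). Power in %:

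| ICC | Reach difference | SD | Continuous | Median split | Three levels, 2 df | Three-level trend |
|---|---|---|---|---|---|---|
| 0.03 | 15 | 0 | 57 | 38 | 35 | 46 |
| 0.03 | 15 | 2 | 46 | 31 | 28 | 38 |
| 0.05 | 15 | 0 | 70 | 48 | 47 | 59 |
| 0.08 | 15 | 0 | 82 | 59 | 58 | 70 |
| 0.08 | 20 | 2 | 78 | 57 | 55 | 67 |

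Over ten settings (these five, plus ICC 0.03 with difference 20 and the other SD value for each pair), the loss was about 8 to 12 points for the trend score. For the median split or 2-df test it was 15 to 25, with the lower end at 14 in a repeat run. Type I error was close to 5% for all four codings.

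**Sensitivity.**
- *Larger effect.* Section 6.1 also uses 15% to 25%. If that is reached at 50% use, the slope is 10/0.5 = 20 points. At the widest spread (ICC 0.08, difference 20, SD 0), power is 97% continuous, 84% median split, 83% three levels on 2 df and 92% trend, so the loss is about 5 to 14. At narrower spreads a 20-point slope barely reduces the loss. At ICC 0.03, difference 15, SD 0 the powers are 77%, 57%, 54% and 66%.
- *Bimodal usage.* Assume half the clinics are near 10% use and half near 67%, with a 15-point slope. Continuous power is 99.6 to 100%, and the grouped tests give 95 to 99.8%, so the loss is about 0 to 5.
- *Starting point fixed.* If continuous usage had 80% power and usage is normal, a four-level trend loses 7.6 points, a three-level trend 11.5, a median split 23.5, three levels on 2 df 24.5, and four levels on 3 df 28.6. Over other usage shapes and starting powers of 50 to 90%, the loss runs from about 4 to 29 points.

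**The case against.** The strongest reply is that the plan never commits to a median split, to three levels, or to a clinic-level dose, so no particular power loss belongs to it. That stands. A reader might infer that the plan gives up 8 to 24 points of power. The documents do not support this. They state no power for this analysis and no distribution of usage across clinics beyond a 50% average, and the loss depends on the number of levels, the test, the effect size and the clinic-by-period variance.

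Usage may also be far more uneven than a normal curve around 50%. Sections 2.2 and 4.6 foresee clinics with high, low, variable, very low or no use, and clinics that stop. With two clear clusters of clinics, levels describe the data well and cost little. That stands too.

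A reader might further infer that the grouped analysis would probably miss a real relationship. That is too strong. With a 20-point slope and the widest spread, every grouped test has over 80% power. In the least favourable setting continuous usage has only 46%, so the main limit there is too little spread in use.

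The calculations test clinic-level changes, whereas the plan fits a patient-level mixed logistic model with a random site effect. They therefore indicate the size of the loss and are not the power of the planned model. Ordered levels also have one merit: they show a pattern without assuming linearity.

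None of this favours levels as the main analysis. Grouping did not gain power in any setting examined, apart from ties when power was near 100%, and leaving the levels undefined adds a choice that could be made after seeing the data.

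**Conclusion.** The point holds as a modest, low-cost improvement. Section 6.3 compares undefined usage levels and plans neither a trend test nor a slope, although objective 2.2.2 asks about dose-response and usage is measured as a proportion. Reading dose as clinic usage is a sound inference, not stated text.

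Under the plan's inputs and an assumed linear 15-point effect, grouping could cost about 8 to 12 points of power (three-level trend) or 14 to 25 (median split or three levels on 2 df). The cost falls to about 5 to 14 points with a 20-point effect at the widest usage spread examined, and to about 0 to 5 if usage is strongly bimodal. These are illustrations. The analysis is exploratory, so no stated power is reduced, and the primary outcome and the overall pre/post comparison are unaffected.

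**What to change.** In Section 6.3, make the main dose-response analysis a period-by-usage interaction in the mixed logistic model. Define usage as the clinic's mPATH-CRC Reach over the visit window of the post-implementation cohort (months 1 to 8), entered as a continuous variable. Report the slope per 10 percentage points of usage with its 95% CI. Add one linearity check, such as a quadratic term, and keep usage groups as a descriptive table or plot. If levels are kept as the main analysis, state the measure, window, unit and cut-points before the data are examined.

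The cost is a short edit to one clause and no new data. The slope assumes rough linearity on the model scale, and with 22 clinics the linearity check will be weak. Usage is not randomised, so the result remains an association under either coding and should be reported as one.

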6.4 Length of Study

Study Timeline

| Study Task | Year 1 | | | | Year 2 | | | | Year 3 | | | | Year 4 | | | | Year 5 | | | | |
|---|--------|----|----|----|--------|----|----|----|--------|----|----|----|--------|----|----|----|--------|----|----|----|---|
| | Q1 | Q2 | Q3 | Q4 | |
| Develop mPATH Implementation Materials | X | | | | | | | | | | | | | | | | | | | | |
| Implementation Focus Groups | X | X | | | | | | | | | | | | | | | | | | | |
| Revise Implementation Materials | | X | | | | | | | | | | | | | | | | | | | |
| Develop and validate EHR queries | | X | X | X | | | | | | | | | | | | | | | | | |
| mPATH-CRC Implementation | | | X | X | X | X | X | X | X | X | X | X | X | X | X | | | | | | |
| Implementation Data Collection | | | | X | X | X | X | X | X | X | X | X | X | X | X | X | X | X | | | |
| Effectiveness Data Collection | | | | | | X | X | X | X | X | X | X | X | X | X | X | X | X | | | |
| Maintenance Data Collection/Clinic Interviews | | | | | | X | X | X | X | X | X | X | X | X | X | X | X | X | | | |
| Data Cleaning | | | | X | X | X | X | X | X | X | X | X | X | X | X | X | X | X | | | |
| Data Analysis and Results Dissemination | | | | | | | | | | | | | | | | | | X | X | X | X |

7.0 Data Management

Clinic survey data will be stored in the Research Electronic Data Capture (REDCap) system, a web-based application for building and managing online surveys and databases. REDCap was developed in the CTSA network and implemented at Wake Forest specifically around HIPAA security guidelines. REDCap provides an intuitive interface for users to enter data, has real-time validation rules at the time of entry, and maintains audit trails.

All extracted clinical datasets and datasets containing data from combined sources will be stored on a central Wake Forest data server using industry standard encryption (e.g., AES-256 bit) to protect personal health information.

All iPad interaction data will be temporarily stored on each iPad using secure Advanced Encryption Standard 256 bit encryption (AES-256) software to protect personal health information. The iPad

EFFECTIVENESS AND IMPLEMENTATION OF MPATH-CRC: A MOBILE HEALTH SYSTEM FOR

COLORECTAL CANCER SCREENING

Wake Forest Baptist Comprehensive Cancer Center (WFBCCC)

WFBCCC # TBD

software automatically sends the data to the central data storage server and removes the data from the iPad after confirmation that the data were sent and received. All study site databases will be stored in an encrypted, HIPAA-compliant Cloud-based server with continuous data backup.

8.0 Confidentiality and Privacy

Confidentiality will be protected by collecting only information needed to assess study outcomes, minimizing to the fullest extent possible the collection of any information that could directly identify subjects, and maintaining all study information in a secure manner. To help ensure subject privacy and confidentiality, only a unique study identifier will appear on the data collection form and in study datasets. An honest broker will mediate the electronic health record data queries to limit the exposure of patient identifying information. Our analyses require us to have full dates of visits (to determine the success of implementation over time), age, and 5-digit zip codes, and GEOIDs (to determine rural or urban residency). Therefore, the honest broker will create a limited data set for analysis. The day that each clinic launches mPATH will be called day 0, with each subsequent or previous date recorded as an integer relative to day 0. This will add additional protections for patients by obscuring dates in the dataset. Any collected patient identifying information corresponding to the unique study identifier will be maintained in a linkage file, stored separately from the data. The linkage file will be kept secure, with access limited to designated study personnel. Subject identifying information will be destroyed three years after closure of the study, consistent with data validation and study design, producing an anonymous analytical data set. Data access will be limited to study staff. Data and records will be kept locked and secured, with any computer data password protected. No reference to any individual participant will appear in reports, presentations, or publications that may arise from the study.

9.0 Data Safety and Monitoring

The only anticipated risks specific to this study are loss of data confidentiality. The mPATH study database is hosted on an encrypted secure server maintained by Wake Forest Information Technology & Services (ITS). The database is password protected, and only authorized individuals are granted access. ITS routinely monitors for any security weaknesses or breaches. In the unlikely event of a data breach, ITS will notify the PI who will convene an internal Data and Safety Monitoring committee to review the event and determine the appropriate response. The Data and Safety Monitoring committee will be comprised of the PI, Project Manager, study statistician, and study programmer. Other individuals may be added to the Data and Safety Monitoring committee at the PI's discretion. In addition, the PI will promptly review any participant or other-reported concerns regarding the study. The PI will report any loss of data confidentiality or other adverse event to the Wake Forest IRB and the NIH within 2 business days of the discovery of the event.

10.0 Reporting of Unanticipated Problems, Adverse Events or Deviations

Any unanticipated problems, serious and unexpected adverse events, deviations or protocol changes will be promptly reported by the principal investigator or designated member of the research team to the IRB and sponsor or appropriate government agency if appropriate.

EFFECTIVENESS AND IMPLEMENTATION OF MPATH-CRC: A MOBILE HEALTH SYSTEM FOR
COLORECTAL CANCER SCREENING
Wake Forest Baptist Comprehensive Cancer Center (WFBCCC)
WFBCCC # TBD

Appendix A – Implementation Strategy Qualitative Study Materials

A.1. Focus Group Invitation Telephone Script (clinics that participated in prior trial)

This is [name of caller] calling on behalf of [name] at Wake Forest Baptist Health. Your clinic was kind enough to participate in his prior study of the mPATH iPad app about colorectal cancer screening. The study showed that the app doubled the number of patients who were screened for colorectal cancer. I'm calling now to invite your clinic to participate in a research focus group to help us learn how mPATH might be implemented in primary care clinics. If you are willing to participate, we would meet with your clinic staff and providers at your clinic site for a group discussion that would last no more than 60 minutes. Each person who participates in the focus group will receive a \$50 gift card as a thank you for their time. We would schedule this meeting for the day and time that works best for your practice. Would you be interested in participating?

[If yes]: Great. What days/times are generally best for your group, and I'll work with you to get the meeting scheduled.

A.2. Focus Group Invitation Telephone Script (clinics that did not participate in prior trial)

This is [name of caller] calling on behalf of [name] at Wake Forest Baptist Health. We have developed an iPad program call mPATH that helps patients get screened for colorectal cancer screening. We recently completed a study that showed the app doubled the number of patients who were screened for colorectal cancer. We now would like to talk to a few practices to figure out how to best implement mPATH in primary care clinics. I'm calling now to invite your clinic to participate in a research focus group to help us learn how to do that. If you are willing to participate, we would meet with your clinic staff and providers at your clinic for a group discussion that would last no more than 60 minutes. Each person who participates in the focus group will receive a \$50 gift card as a thank you for their time. We will not ask your clinic to implement mPATH. We simply want to hear your opinions about how clinics might use it in the future. We would schedule this meeting for the day and time that works best for your practice. Would you be interested in participating?

[If yes]: Great. What days/times are generally best for your group, and I'll work with you to get the meeting scheduled.

EFFECTIVENESS AND IMPLEMENTATION OF MPATH-CRC: A MOBILE HEALTH SYSTEM FOR
COLORECTAL CANCER SCREENING
Wake Forest Baptist Comprehensive Cancer Center (WFBCCC)
WFBCCC # TBD

A.3. Implementation Strategy Focus Group Moderator's Guide (Wake Forest Clinics)

FG Purpose: To learn how mPATH can be implemented successfully in primary care clinics.
The main overarching questions to answer are:

1. What would make clinic staff want to use mPATH with patients?
2. How do clinic staff think mPATH would be best incorporated into clinic flow?
3. What type of training and support will clinics need to use mPATH?

The guide will:

- I. Explore the facilitators and barriers to implementation
- II. Strategies for minimizing barriers
- III. The adequacy of draft training materials
- IV. Additional support or training materials desired
- V. Focus groups will also comment on the set of clinic check-in questions proposed for the mPATH-CRC iPad app

Focus groups will be audio recorded and the content summarized. Revisions to the implementation strategy and materials will be informed by the focus group results.

Date:

Moderator(s):

Note Taker(s):

Start time:

End time:

I. WELCOME

Hello and welcome to our session. My name is [name]. I am today's focus group moderator. This is [name]; she will be assisting with the focus group. She will record our discussion and take notes on what we say, to ensure we don't miss anyone's comments.

We want to thank you for being here today. We appreciate your willingness to share your thoughts with us. The reason you are here today is obtain your feedback about a program called mPATH. mPATH is a user-friendly iPad program designed to increase the efficiency and quality of care in primary care offices. While in the waiting room, patients use mPATH to

EFFECTIVENESS AND IMPLEMENTATION OF MPATH-CRC: A MOBILE HEALTH SYSTEM FOR
COLORECTAL CANCER SCREENING
Wake Forest Baptist Comprehensive Cancer Center (WFBCCC)
WFBCCC # TBD

answer standard check-in items and assess their need for routine cancer screening. mPATH then transmits this information to the electronic health record, reducing data entry by nursing staff.

Our goal today is to obtain your opinions about how best to implement mPATH into a primary care clinic's workflow. I will be asking for your feedback about the iPad program, our proposed clinic workflow strategy and our training plan. There are no right or wrong answers. Everything we talk about will be considered confidential. We will use the information from our conversations to inform our study team about the best way to implement mPATH in other clinics. There will not be any names used and no one outside of this room will know specifically who said what. Please do not share other people's names or comments outside of the group. We will audio record today's conversation and take notes. This helps us remember what you all said. The notes and the audio will be kept in our offices and will not be shared with anyone outside our project.

You will be asked to complete a brief paper questionnaire at the end of our group discussion, and you will each receive a \$50 gift card for your participation today. I will send around a sheet where I will collect your information, so I can make sure that everyone who is here receives their gift card for participation.

The session should last between 30-45 minutes. Before we get started, are there any questions?

We would like for you to speak freely, sharing your ideas and opinions, even if they are different from others.

There are no right or wrong answers.

All your views are important, whether positive or negative.

We want to get as many different points of view as we can.

Please remember to silence your cell phones!

Since this is a group discussion, you do not have to wait for me to call on you to speak, but please try to speak one at a time. As I mentioned, we will be taking written notes as well as

EFFECTIVENESS AND IMPLEMENTATION OF MPATH-CRC: A MOBILE HEALTH SYSTEM FOR
COLORECTAL CANCER SCREENING
Wake Forest Baptist Comprehensive Cancer Center (WFBCCC)
WFBCCC # TBD

recording the session. This is to make sure that we do not miss anyone's comments. Is that okay with everyone?

OK, first, let's go around the room and say your first name and your favorite thing to do on a warm summer day.

II. MAIN QUESTIONS

Let's get started.

Motivators and Barriers

First, let me demonstrate the mPATH iPad program so you can see how it looks and how we are thinking clinic staff will use it.

1. What are your first impressions of this program?

Follow-up question:

- a. Based on what you've seen in the demonstration, tell me what about it would be helpful to you in your clinic.
- b. Tell me what would not be helpful.

2. What would motivate your team to use this iPad app?

Follow-up questions:

- a. We programmed the app to ask patients the standard clinic check-in questions, hoping that would save nurses some time. Do you think that feature is helpful or not helpful?
(probe): Tell me why you say that.

- b. What else could the app do that would make your job easier and make you excited to use it?

3. What would make you not want to use it?

EFFECTIVENESS AND IMPLEMENTATION OF MPATH-CRC: A MOBILE HEALTH SYSTEM FOR
COLORECTAL CANCER SCREENING
Wake Forest Baptist Comprehensive Cancer Center (WFBCCC)
WFBCCC # TBD

4. Patients will independently answer the check-in questions on the iPad, and the program will transmit the answers to the standard nursing check-in note in WakeOne. The nurses will get to see the patient's answers in the WakeOne note before they sign off on the note.

What are your thoughts about that process?

(probe):Tell me about any concerns you may have.

Clinic Workflow

I am going to walk you through what we are envisioning to be the typical pattern of patient check in and how staff and patients will hand off and use the iPad.

(Display clinic workflow poster/slide illustration and walk through the flow.)

5. What are your immediate thoughts about this workflow?

Follow-up questions:

- a. What do you like about the workflow? And why?
- b. What don't you like about the workflow? And why?
- c. Are the front desk staff the best people to hand the iPad to patients? Why or why not?

6. The app includes audio narration and a video about colon cancer screening. If we gave patients disposable earbuds when they are handed the iPad, do you think they could use the app in the waiting room? Why or why not?

Follow-up questions:

- a. Do you think audio in the video is important? Or do you think reading closed captions would be enough?
- b. How could patients use the app without earbuds? Would it disturb other patients?

EFFECTIVENESS AND IMPLEMENTATION OF MPATH-CRC: A MOBILE HEALTH SYSTEM FOR
COLORECTAL CANCER SCREENING
Wake Forest Baptist Comprehensive Cancer Center (WFBCCC)
WFBCCC # TBD

7. What is the longest time you think patients could use the app before it would interfere with clinic flow?

Follow-up questions

- a. On average, how long do patients wait from check-in until the doctor sees them?
8. How many iPads would a clinic of your size and patient volume need to ensure this process didn't interfere with patient flow?
9. If a patient is 50 or older, the app will determine if they are due for colon cancer screening. If they are due, it will help them get a test ordered. If your clinic decided to use this program, would it be best to offer it to all patients on check-in, or only those who are 50 and older? Why?

Training and Support

In a few months, we will be helping some clinics incorporate the mPATH program into their workflow. Now I will tell you about the training and support we are planning to give those clinics so you can tell me what you think about our plans.

We will first ask each clinic to identify a person working in the clinic, a “clinic champion,” who will help keep the program going and serve as our main contact. If the clinic wants us to add additional check-in questions to the mPATH program, we can do that for them. We will also hold a 45 minute on-site training session with the clinic staff to give them practice using the mPATH program. Afterwards, we will provide the clinics with as needed technical support by phone, email, or in person.

10. What do you think about this training plan?

- a. Follow-up questions: What would work well? What could be better?

11. How do you suggest we find the right person for the “clinic champion” role?

EFFECTIVENESS AND IMPLEMENTATION OF MPATH-CRC: A MOBILE HEALTH SYSTEM FOR
COLORECTAL CANCER SCREENING
Wake Forest Baptist Comprehensive Cancer Center (WFBCCC)
WFBCCC # TBD

Follow-up questions:

- a. Who would we contact to find a champion?
- b. If your clinic decided to use this program, who at your clinic would be the champion? What is his/her role here?

12. How much time is reasonable for you to attend an on-site training session?

Follow-up question:

- a. If we were to hold a training session for your clinic, when would be the best time for that?

13. Do you think most clinic staff would watch a webinar or on-line video that provides an overview of the program prior to the training session?

Follow-up questions:

- a. Is this something staff could do during free time at work (like during lunch or other free time)?
- b. What would be a reasonable length of time for a webinar or on-line video?

14. What is the best way for the clinic champion to communicate with us if the clinic needs technical support or help?

- a. (Prompt:) by phone, email, text, video chat?
- b. Follow-up question: What is a reasonable time for us to be able to reply or respond back to clinic champions when they have technical or other questions?

III - CLOSING

EFFECTIVENESS AND IMPLEMENTATION OF MPATH-CRC: A MOBILE HEALTH SYSTEM FOR

COLORECTAL CANCER SCREENING

Wake Forest Baptist Comprehensive Cancer Center (WFBCCC)

WFBCCC # TBD

- You have all had a lot of really important things to say, and I appreciate your openness and willingness to share. Would anyone like to share any other comments before we end?

Provide participants with questionnaires and ask that they complete them on paper. Then, give \$50 to participant and have them sign saying they received it.

EFFECTIVENESS AND IMPLEMENTATION OF MPATH-CRC: A MOBILE HEALTH SYSTEM FOR
COLORECTAL CANCER SCREENING
Wake Forest Baptist Comprehensive Cancer Center (WFBCCC)
WFBCCC # TBD

A.4. Implementation Strategy Interview Guide (Wake Forest Clinics)

Interview Purpose: To learn how mPATH can be implemented successfully in primary care clinics. The main overarching questions to answer are:

1. What would make clinic staff want to use mPATH with patients?
2. How do clinic staff think mPATH would be best incorporated into clinic flow?
3. What type of training and support will clinics need to use mPATH?

The guide will:

- VI. Explore the facilitators and barriers to implementation
- VII. Strategies for minimizing barriers
- VIII. The adequacy of draft training materials
- IX. Additional support or training materials desired
- X. Interviews will also comment on the set of clinic check-in questions proposed for the mPATH-CRC iPad app

Interviews will be audio recorded and the content summarized. Revisions to the implementation strategy and materials will be informed by the interview results.

Date:

Interviewer:

Start time:

End time:

I. WELCOME

I want to thank you for speaking with me today. I appreciate your willingness to share your thoughts with me. The reason we are doing this interview is obtain your feedback about a program called mPATH. mPATH is a user-friendly iPad program designed to increase the efficiency and quality of care in primary care offices. While in the waiting room, patients use mPATH to answer standard check-in items and assess their need for routine cancer screening. mPATH then transmits this information to the electronic health record, reducing data entry by nursing staff.

